3.2 Final Analysis

The final analysis will be performed when all participants have completed trial.

Statistical Analysis Plan

4 STATISTICAL METHODS

4.1 General Considerations for Data Analyses

All statistical calculations will be primarily performed using SAS[®] System Version 9.4 or higher. Analysis results will be presented using descriptive statistics. For categorical variables, the number and percentage of participants in each category will be presented; for continuous variables, the number of participants (n), mean, standard deviation (SD), median, first quartile (Q1), third quartile (Q3), minimum, and maximum will be presented.

For additional details on data presentation, refer to the Statistical Programming Plan (SPP).

4.1.1 Definition of Baseline

Unless otherwise specified, baseline is defined as the last non-missing valid observation prior to the first dose of investigational product (IP). In cases where baseline measurements are taken on the same day as IP and no times are reported, it will be assumed that these measurements are taken prior to IP being administered.

4.1.2 Analysis Windows

Analysis visit windows will be used for all visit-based assessments to map longitudinal observations to scheduled visits and thereby allow for by-visit analyses, since not all assessments are performed on the scheduled day. Unless otherwise specified, all longitudinal efficacy, safety, and biomarker data analyses will be based on the analysis visit windows. The analysis visit windows will be calculated by bisecting the interval between adjacent scheduled visit days except for the first post-treatment visit. The first post-treatment visit will start at Day 2. The detailed analysis visit windows will be specified in SPP.

The actual assessment day will be mapped to the windows defined for each scheduled study visit with following rules:

- If more than one assessment falls within a visit window, the closest non-missing assessment to the scheduled day will be used in the analysis.
- If 2 non-missing assessment actual dates are equidistant from the target day, the later visit will be used in the analysis.
- For retest values of laboratory data, the retest value will be chosen.

All observations will be included in data listings.

4.1.3 Missing Data

In general, missing data will not be imputed unless methods for handling missing data are specified.

4.2 **Protocol Deviations**

The protocol deviations are reviewed and categorized as major and minor prior to the database lock. The number and percentage of participants with major protocol deviations by

Daxdilimab (HZN-7734) HZNP-DAZ-201 Statistical Analysis Plan

deviation reason (eg, nonadherence to study drug, violation of select inclusion/exclusion criteria) will be summarized. A by-participant listing will be provided for all protocol deviations.

A by-participant listing will be provided for those participants who did not meet at least one eligibility (inclusion or exclusion) criterion. The listing will present the eligibility criterion (or criteria if more than one deviation) that participants did not meet and related comments, if collected.

4.3 Analysis Sets

4.3.1 Safety Analysis Set

The safety analysis set is defined as participants who received any dose of daxdilimab. The efficacy, safety, pharmacodynamics (PD) and immunogenicity analyses will be based on the safety analysis set.

4.3.2 Pharmacokinetic Analysis Set

The Pharmacokinetic (PK) analysis set is defined as participants who received any dose of daxdilimab and have at least one measurable PK concentration post dose. The PK analyses will be based on PK analysis set.

4.4 Subject Disposition

A summary of subject disposition will be presented using the categories presented below.

- Screened
- Screen failed with reasons
- Enrolled
- Enrolled but not treated
- Enrolled and treated
- Completed treatment
- Discontinued treatment with reasons
- Completed trial
- Discontinued trial with reasons

4.5 Investigational Product Exposure

The number of doses received, amount of the investigational product (IP) received, durations of the IP exposure, and treatment compliance will be summarized for the safety analysis set. The number and percentage of participants treated ≥ 4 weeks, ≥ 12 weeks, ≥ 24 weeks, and ≥ 36 weeks will also be provided.

• Durations of the study drug exposure = last dose date + 28 -first dose date + 1.

Statistical Analysis Plan

- The amount of study drug exposure: if a participant received partial dose at a dosing visit, then the amount of IP at that dosing visit will be estimated based on the actual volume administered.
- Treatment compliance for an individual participant = [Total number of doses received]/[Total number of doses planned per protocol] ×100%.

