1 PROTOCOL SUMMARY

1.1 Synopsis

Name of Sponsor/Company:	Name of Investigational Product:	Name of Active Ingredient:							
Horizon Therapeutics Ireland DAC	Daxdilimab (HZN-7734)	Daxdilimab (HZN-7734)							
Protocol Title:									
A Phase 2a, Open Label, Proof-of-Concept Trial of Daxdilimab for the Treatment of Moderate-to-Severe Alopecia Areata									
Phase of Development:									
Phase 2a									
Trial Center(s):									
This trial will be conducted at ap	proximately 8 sites located in Canada	and the United States.							
Number of Participants (plann	ed):								
The trial is planned to enroll app	roximately 30 participants with alopec	ia areata (AA).							
Duration of Trial:									
screening period, 32 weeks for daxdilimab mg	participant is approximately 52 weeks or the open-label treatment period w follow-up period.								
Investigational Product, Dosag	e, and Mode of Administration:								
Daxdilimab will be provided as	s a								
All participants will receive daxdilimab mg administered subcutaneously as two 1.5 mL injections All investigational product (IP) administration will be done at the clinical site by the trial staff. On and and participants will remain under observation for at least 1 hour after IP administration.									
Reference therapy, dosage and	mode of administration:								
Not applicable (N/A).									

Name of Sponsor/Company:	Name of Investigational Product:	Name of Active Ingredient:					
Horizon Therapeutics Ireland DAC	Daxdilimab (HZN-7734)	Daxdilimab (HZN-7734)					
Objectives and Endpoints:							
Primary Objective and Endpo	int						
Efficacy Objective	Efficacy Endpoint						
To evaluate the effect of daxdilimab on reducing hair loss at Week 24 in participants with AA.	ing hair score at Week 24.						
Secondary Objectives and End	lpoints						
Efficacy Objectives	Efficacy Endpoints						
To evaluate the effect of daxdilimab on reducing hair loss through 9 months of treatment in participants with AA.	SALT from baseline at Week	no achieve ≥50% reduction in					
To evaluate the post-treatment duration effect of daxdilimab on reducing hair loss in participants with AA.	 Percent change from baseline Weeks 40-48. Proportion of participants wh SALT from baseline at Week 	no achieve ≥50% reduction in					
	 Proportion of participants with absolute SALT score ≤ 10, 20, 30, 50 at Weeks 40-48. 						
Pharmacokinetic (PK)/ Pharmacodynamic (PD)/ Immunogenicity Objectives	PK/PD/Immunogenicity Endpoints	5					

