occur during the Week 24 visit. All participants will have a follow-up period of 16 weeks (through Week 48) to evaluate long-term safety and to observe the duration of efficacy following the treatment period. Participants who prematurely stop dosing will be followed through Week 48 unless participants withdraw consent of trial participation or are lost to follow-up. Any participant who discontinues from the trial prematurely and does not plan to participate in the post-treatment follow-up period will be requested to complete the early termination (ET) visit.

For scheduled trial visits, participants will come to the trial centers on 14 occasions: screening,

Efficacy will be evaluated by assessment of SALT scores,

Blood samples will be collected from all participants to characterize the PK, PD, and immunogenicity of daxdilimab.

Safety will be assessed by collecting AEs, SAEs, AESIs, performing local injection site tolerability assessment, recording vital signs, performing physical examinations and ECGs, and evaluating clinical laboratory results.

Inclusion/Exclusion Criteria:

Inclusion Criteria

All participants must meet all of the following criteria to be eligible for trial participation, either at the screening and Day 1 visits, or only at one of the specified visits (screening or Day 1) as noted in the criterion:

- 1. Written informed consent and any locally required authorization (eg, Health Insurance Portability and Accountability Act in the United States,) obtained from the participant prior to performing any protocol-related procedures, including screening evaluations.
- 2. Adult men and women, aged 18 to 65 years, inclusive, at the time of informed consent.
- 3. Willing and able to comply with the prescribed treatment protocol and evaluations for the duration of the trial.
- 4. Willing to keep the same hair style and color (eg, hair products, process, and timing for hair appointments) for the duration of the trial.
- 5. Clinical diagnosis of moderate-to-severe AA defined as the presence of ≥ 50% and ≤95% total scalp hair loss at screening and baseline (Day 1) defined by the SALT score.
- Duration of current episode of hair loss >3 months but <7 years at screening and Day 1, along with investigators' assessment that hair regrowth is possible. Total duration since diagnosis of AA could be >7 years.

Page 17 of 70

Name	of Sponsor/Company:	Name of Investigational Product:	Name of Active Ingredient:				

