Abbreviations: ADA, anti-drug antibodies; AE, adverse event; AESI, adverse event of special interest; anti-HBc, antibody to hepatitis B core antigen; ALODEX, Alopecia Density and Extent; HBsAg, Hepatitis B surface antigen; ClinRO, Clinician Reported Outcome; DC, dendritic cell; ECG, electrocardiogram; EOT, end of treatment; ET, early termination; HBcAb, hepatitis B core antibody; HBV, hepatitis B virus; HCV, hepatitis C virus; HIV, human immunodeficiency virus; IFN, interferon; IP, investigational product; MxA, myoxvirus protein A; PBMCs, peripheral blood mononuclear cells; PK, pharmacokinetic; PPD, purified protein derivative; Q4W, every 4 weeks; SAE, serious adverse event; SALT, Severity of Alopecia Tool; SC, subcutaneous; TB, tuberculosis; Wk, week; WOCBP, women of childbearing potential.

¹ Participants who prematurely stop dosing will enter the post-treatment follow-up period of 16 weeks after the last dose received. Participants who do not enter the post-treatment follow-up period will be requested to complete the ET visit.

² A focused physical examination should be performed as described in Section 8.5.2.

³ Vital signs comprise heart rate, blood pressure, temperature, and respiratory rate. Vital signs will be performed pre-dose during the Treatment Period.

⁴ Laboratory tests will be performed pre-dose during the Treatment Period.

⁵ 12-lead ECG to be done pre-dose during the Treatment Period.

⁶ WOCBP (see Section 5.1 for definition) will have a serum pregnancy test at screening and urine pregnancy tests at other visits.

⁷ The results of an IFN-gamma release assay (ie, QuantiFERON-TB Gold performed within 12 weeks of the Screening visit (if available) are acceptable, provided there is no reason to suspect any re-exposure. If PPD is used, a second visit will be necessary for PPD reading only.

⁸ Medical photographs of the full scalp will be taken for all participants, and of the eyebrows and eyelashes for participants who have hair loss in these areas at baseline.

⁹ Participants will receive daxdilimability administered SC on Day 1 followed by All IP administrations will be done at the clinical site by the trial staff. On and and a participants will remain under observation for at least 1 hour after IP administration.

PRIVATE AND CONFIDENTIAL INFORMATION OF HORIZON THERAPEUTICS IRELAND DAC

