6 TREATMENT

6.1 Trial Treatment Administered

This trial involves SC administration of daxdilimab mg (two 1.5 mL injections) The IP will be administered by trial site staff in the clinic. On Day 1 and participants will remain under observation for at least 1 hour after IP administration. The IP will be provided by the sponsor. Further details regarding the IP can be found in Table 2.

Table 2: Trial Treatment

	Investigational Product
Product name	Daxdilimab
Dosage form	
Source of procurement	Horizon Therapeutics
Unit dose strength(s)/Dosage level(s)	mg dose, administered as 2 x 1.5 mL SC injections.
Route of Administration	Subcutaneous, (total of 9 doses)
Physical description	
Dosing instructions	Daxdilimab should be administered by clinic staff trained in best practices for SC administration of treatments. More details on the administration method are described in the study manual.
Abbreviations: ; SO	, subcutaneous.

The contents of the label will be in accordance with all applicable regulatory requirements.

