3 PLANNED ANALYSES

3.1 Primary Analysis

The primary analysis will be performed when all participant have completed Week 24 or withdraws prior to the scheduled Week 24 visit. All available data on or before the data cut-off (including data collected after Week 24) will be included in the primary analysis.

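### SAP 4.5 divides doses received by all nine planned doses with no limit at the data cut-off, so at a Week 24 primary analysis doses not yet due would count as missed

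*SAP*

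**What the plan says.** - **Compliance.** SAP 4.5 gives one formula for each participant, "Total number of doses received]/[Total number of doses planned per protocol", expressed as a percentage. It does not mention the data cut-off or early discontinuation of treatment.
- **Number of doses.** Table 2 in Protocol 6.1 gives a "total of 9 doses".
- **Timing.** SAP 3.1 states: "The primary analysis will be performed when all participant have completed Week 24", or have withdrawn before that visit. It brings in all data up to the cut-off, including data after Week 24. A final analysis follows when all participants have completed the trial (SAP 3.2).
- **Exposure.** The duration formula in SAP 4.5 begins "Durations of the study drug exposure = last dose date + 28", then subtracts the first dose date and adds 1. It is tabulated as at least 4, 12, 24 and 36 weeks. It too makes no reference to the cut-off.

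**The concern.** Treatment continues after Week 24. When the last participant reaches the primary endpoint visit, that participant and others enrolled shortly before still have scheduled doses ahead of them. With a fixed denominator of nine, a dose that could not yet have been given looks the same as one that was missed.

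Dosing is on site and under the investigator's direct control (Protocol 6.3.2), so true compliance should be high. A shortfall created by the definition would stand out and could be read as poor adherence next to the primary result. The exposure formula has the opposite fault: at a cut-off soon after a dose, it credits treatment time that has not yet passed.

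**Working it through.** **Inputs**
- Planned doses: 9 (Protocol 6.1, Table 2).
- Treatment period: 32 weeks (Protocol 1.1, "screening period, 32 weeks for" the open-label treatment period).
- Dosing interval: not in the public text; taken as 28 days.
- Week 24 dose: assumed given at the Week 24 visit, before the cut-off.

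**Does a 28-day interval reproduce the plan's own figures?**
- Doses: 32/4 + 1 = 9 (Day 1, then Weeks 4 to 32). This matches Table 2.
- Visits: screening + Day 1 + 12 four-weekly visits (Weeks 4 to 48) = 14. Protocol 1.1 says "participants will come to the trial centers on 14 occasions".
- Protocol 8.5.5 notes that no product is given at Week 36, which fits a last dose at Week 32.
- The Schedule of Assessments footnotes define "Q4W, every 4 weeks", and SAP 4.5 adds 28 days after the last dose.

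Every visible figure fits.

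**Compliance for a participant who has missed nothing**

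SAP 4.5 gives doses received / 9. The alternative is doses received / doses scheduled up to the cut-off.

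| Last dose due before cut-off | Doses received | SAP 4.5 | Denominator limited to cut-off |
|---|---|---|---|
| Week 24 | 24/4 + 1 = 7 | 7/9 = 77.8% | 7/7 = 100% |
| Week 28 | 28/4 + 1 = 8 | 8/9 = 88.9% | 8/8 = 100% |
| Week 32 | 32/4 + 1 = 9 | 9/9 = 100% | 9/9 = 100% |

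The individual shortfall is therefore 22.2, 11.1 or 0 percentage points.

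**Effect on the mean.** The documents give no accrual pattern, so only a range is possible. Take 30 fully adherent participants. If only the last one is between Weeks 24 and 28, the mean is (29 × 100 + 77.8)/30 = 99.3%, or 0.7 points low. If all 30 were in that interval, it would be 22.2 points low.

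**Early discontinuation.** The formula does not single out this case. A participant who stops after three on-time doses scores 3/9 = 33.3% if later doses stay in the denominator, and 3/3 = 100% if they do not. Either is defensible, but they answer different questions.

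**Exposure duration at the cut-off**

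Credited days = (last dose − first dose) + 28 + 1. Elapsed days = (cut-off − first dose) + 1. With the last dose on the cut-off day itself:

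| Last dose | Credited | Elapsed | Row credited | Row by elapsed time |
|---|---|---|---|---|
| Week 24 | 168 + 29 = 197 | 169 | ≥24 weeks | ≥24 weeks |
| Week 28 | 196 + 29 = 225 | 197 | ≥24 weeks | ≥24 weeks |
| Week 32 | 224 + 29 = 253 | 225 | ≥36 weeks (252 days) | ≥24 weeks |

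Up to 28 days can be credited ahead of time. In these cases the row changes only after a Week 32 dose.

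**Exposure rows without a cut-off.** On the nominal schedule, 1, 3, 6 and 9 doses give 29, 85, 169 and 253 days against thresholds of 28, 84, 168 and 252. Each is met with one day to spare.

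**The case against.** The strongest reply is that little depends on this. SAP 4.5 does not say that the compliance table is produced at the primary analysis; that is inferred from the use of all available data. The same section reports number of doses and duration, and SAP 4.4 reports completion and discontinuation of treatment, so a careful reader could tell pending doses from missed ones. Efficacy is analysed in everyone dosed (SAP 4.3.1), with no adherence-based exclusion. A programmer might also take *planned* to mean *due*. All of this limits the importance of the point. It does not remove it, because the written formula, followed literally, gives the wrong percentage.

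A reader might infer more, but the documents do not support it:
- **That the exposure rows misclassify participants on schedule.** They do not, as the nominal figures show. A participant with all nine doses would leave the top row only if the last dose came two or more days early relative to Day 1, and the visit windows are not in the public text.
- **That a 36-week row conflicts with a 32-week treatment period.** Nine doses, each credited with 28 days, cover 9 × 28 = 252 days, or 36 weeks. This agrees with the nine months of treatment named in the objectives. A ≥4-week row that every dosed participant meets is uninformative, but not an error.
- **That a partial dose is scored as a full one.** SAP 4.5 is silent on this for compliance and estimates amount received separately from the volume given. Weighting compliance by volume is a preference.
- **That low compliance would be used to explain weak efficacy.** Neither document plans such an analysis.

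**Conclusion.** The point holds for the compliance denominator and, secondarily, for the uncapped exposure duration. At the primary analysis, a fully adherent participant would be reported at 77.8% or 88.9% if the Week 28 or Week 32 doses, respectively, were not yet due.

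The result rests on three assumptions: 4-weekly dosing, the exposure table being produced at the primary analysis, and some participants not having reached Week 32 at the cut-off. The size of the effect on the summary cannot be fixed without the accrual pattern. Participants past the Week 32 dose show the correct figure, and no dose is pending at the final analysis. No efficacy estimate is affected. This is a minor defect in a definition.

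**What to change.** Amend SAP 4.5 in three places:
1. Define the compliance denominator as the number of doses scheduled per protocol up to the data cut-off, which is 9 at the final analysis.
2. State whether doses scheduled after treatment discontinuation stay in the denominator.
3. Cap duration at the cut-off: the earlier of (last dose date + 28) and the cut-off date, minus first dose date, plus 1.

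Keep the +1 and the existing rows. Dropping the +1 would remove the one-day margin at every threshold. A ≥32-week top row would be met by eight doses (196 + 28 = 224 days, even without the +1), so it would no longer identify full treatment.

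The cost is a few lines of SAP text and a small programming change before the primary analysis database lock. No additional data are needed.

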4.6 Demographics, Baseline Characteristics, and Medical History

The demographics (age, gender, race, ethnicity, height, weight, and body mass index) will be summarized.

Participant background information, including baseline SALT,

Significant medical history finding will be summarized by MedDRA system organ class (SOC) and preferred term (PT).

4.7 Efficacy Analyses

4.7.1 Primary Efficacy Endpoint and Analysis

4.7.1.1 Primary Efficacy Endpoint

The primary efficacy endpoint is the percent change from baseline in SALT score at Week 24.

4.7.1.2 Primary Efficacy Analysis

The primary efficacy endpoint of percent change from baseline in SALT score at Week 24 will be summarized using descriptive statistics. A 2-sided 95% confidence interval will be calculated for the mean.

4.7.1.3 Handling Plan for Prohibited Medication Use and Treatment Discontinuation

The results after administration of the prohibited medications that are considered to be effective for treatment of AA, will be imputed using the worst observation on or prior to administration of the prohibited medications including baseline. The prohibited medications that are considered to be effective for treatment of AA will be identified and finalized by medical monitor before database lock of each planned analysis.

Participants who discontinue treatment early will be asked to come to scheduled evaluations until the end of the study unless participants withdraw consent of trial participation or are lost to follow-up. The data collected after discontinuation of study treatment will be included in the analysis.

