6.4 Concomitant Therapy

All medications (including over-the-counter drugs, vitamins, herbal/natural products, and antacids) taken within 4 weeks prior to screening and throughout the trial must be recorded. In addition, the use of any prohibited medications must be recorded within the timeframe described in the exclusion criteria. No rescue medications or treatments are permitted in this study.

Medication entries may be captured as generic or trade names. Trade names should be used for combination drugs. Entries should include as much as possible of the following information: the dose, unit, frequency of administration, route of administration, start date, end date, and indication. If the medication is stopped or the dosage is changed, these details must be recorded.

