6.4.2 Prohibited Therapies or Procedures

Participants who start prohibited medications or therapies that have been demonstrated to be effective for treatment of AA during the trial will be withdrawn from trial treatment. Participants who start prohibited medications or therapies for other reasons during the trial may be withdrawn from trial treatment if an impact on efficacy assessment or safety of the participants is expected. If in any doubt, investigators are advised to discuss medications with the medical monitor. Table 3 lists prohibited medications that are not to be used from the defined washout periods before the first administration of trial treatment at the Day 1 visit through the last trial visit.

Prohibited medications, products, and procedures	Washout period prior to first dose (Day 1)
Any pDC inhibiting therapies (eg, anti-ILT7, anti-BDCA2).	Lifetime
History or presence of hair transplants.	Lifetime
Micropigmentation of the scalp (Note: microblading of the eyebrows is permitted).	Lifetime
Any biologic B-cell-depleting therapy (eg, rituximab, ocrelizumab, or ofatumumab) or other B-cell targeting therapy (eg, belimumab).	12 months
Any marketed or investigational biological agent.	12 weeks or 5 half-lives, whichever is longer
Platelet-rich plasma injections.	12 weeks
Transfusion with blood products, packed red blood cells, platelets or treatment with plasmapheresis, or plasma exchange.	8 weeks
Any biologic or conventional DMARD, immunosuppressant (eg, cyclosporine, methotrexate, or azathioprine), JAK-inhibitor, IFN blocking therapies, or antiproliferative agents.	8 weeks or 5 half-lives whichever is longer
Live and live attenuated vaccines.	8 weeks

Table 3: Prohibited Therapies or Procedures

Prohibited medications, products, and procedures	Washout period prior to first dose (Day 1)
Nonbiological investigational product or device.	4 weeks or 5 published half-lives, whichever is longer
Nonlive and nonlive-attenuated vaccines for COVID-19 (eg, RNA-based vaccines, protein-based vaccines, and nonreplicating viral vector-based vaccines).	4 weeks prior to Day 1 and within 2 weeks prior to each trial visit
PUVA treatment, UV-B phototherapy (including tanning beds) or excimer laser, excessive sun exposure or has used tanning booths.	4 weeks

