9.3.2.3 Handling Plan for Prohibited Medication Use

For participants who take prohibited medications that are considered to be effective for treatment of AA, the result after administration of the prohibited medications will be imputed using the worst observation, including baseline for continuous endpoints. The participants will be considered non-responder after administration of the prohibited medications for binary endpoints.

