4.7.2.2 Secondary Efficacy Analyses

The continuous secondary efficacy endpoints will be summarized in the same way as the primary efficacy endpoint, including handling plan for prohibited medication use, treatment discontinuation and missing data (Section 4.7.1.3 and Section 4.7.1.4). Spaghetti plots of SALT score by participant over time will be presented. In addition, percent change from baseline in SALT score over time will be analyzed by baseline IFN gene signature levels (high versus low).

The binary secondary efficacy endpoints will be summarized descriptively using frequencies and percentages. A 2-sided 95% confidence interval will be calculated for the percentage. The participants will be considered non responder after administration of the prohibited medications that are considered to be effective for treatment of AA. The data collected after discontinuation of study treatment will be included in the analyses. Missing visits due to skipped visits will be imputed using the last observation carred forward (LOCF), and the participants will be considered non-responders after early dropout of study.

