4.8.4 Prior and Concomitant Medications

Medications collected at screening and during the trial will be coded using the current version of the World Health Organization Drug dictionary (WHO-DD). Number (%) of participants who received prior medications and concomitant medications will be summarized by WHO-DD Anatomical Therapeutic Chemical (ATC) category and PT. At each level of summarization, a participant is counted once if the participant reported one or more medications at that level. The prior and concomitant medications are defined as below.

- Prior medications are defined as medications with a stop date occurring before the IP administration date.
- Concomitant medications are defined as medications with a start date on or after the IP administration date or stop date occurring on or after the IP administration date.

The number and percentage of participants who take prohibited medications that are considered to be effective for treatment of AA will also be summarized by WHO-DD ATC category and PT.

The missing start/stop date will be imputed as appropriate and the details of the imputation will be included in the SPP.

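### The rule that sets aside SALT values after outside alopecia treatment is worded for medications, so values after prohibited procedures such as phototherapy or excimer laser may be kept as observed

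*SAP*

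**What the plan says.** Three sections carry the rule.

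- SAP 4.7.1.3, for continuous SALT endpoints, replaces "The results after administration of the prohibited medications that are considered to be effective for treatment of AA" with the worst value seen up to that point, baseline included. This governs the primary analysis: "The primary efficacy endpoint is the percent change from baseline in SALT score at Week 24".
- SAP 4.7.2.2, for responder endpoints: "The participants will be considered non responder after administration of the prohibited medications that are considered to be effective for treatment of AA".
- Protocol 9.3.2.3 covers both endpoint types with the same trigger: "For participants who take prohibited medications that are considered to be effective for treatment of AA".

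SAP 4.7.1.3 adds that the medical monitor settles which items count before each database lock. Data collected after stopping daxdilimab stay in the analysis (Protocol 9.3.2.4, SAP 4.7.1.3).

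Protocol 6.4.2 is broader. Its title refers to therapies and procedures, its withdrawal-from-treatment sentence applies to "Participants who start prohibited medications or therapies that have been demonstrated to be effective for treatment of AA during the trial", and the column heading of Table 3 names products and procedures alongside medications. The table includes "PUVA treatment, UV-B phototherapy (including tanning beds) or excimer laser", and also platelet-rich plasma, hair transplants and scalp micropigmentation.

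On data capture, Protocol 6.4 requires all medications taken during the trial to be recorded and adds that "the use of any prohibited medications must be recorded within the timeframe described in the exclusion criteria". On reporting, SAP 4.8.4 relies on drug-dictionary coding (WHO-DD, at ATC and preferred-term level) and says: "The number and percentage of participants who take prohibited medications that are considered to be effective for treatment of AA will also be summarized".

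**The concern.** The rule exists so that hair regained through another treatment is not credited to daxdilimab. If it reaches only drugs, it misses non-drug treatments that the protocol itself prohibits. The trial is open-label with a single arm, so no control group would carry the same error and offset it. The error would usually favour the drug, in the primary mean and in each responder rate. The open scope would also be settled by judgement before each database lock, in a trial where treatment is known and SALT results can be seen, and the answer could differ between the primary and final analyses.

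**Working it through.** **1. Scope of the wording, side by side**

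| Place | Scope |
|---|---|
| Protocol 9.3.2.3; SAP 4.7.1.3; SAP 4.7.2.2 (efficacy rules) | medications |
| SAP 4.8.4 (reporting) | medications, coded by WHO-DD |
| Protocol 6.4 (recording) | medications |
| Protocol 7.1.1 (stopping daxdilimab) | medications, with a pointer to 6.4.2 |
| Protocol 6.4.2, withdrawal sentence | medications or therapies |
| Protocol 6.4.2, sentence introducing Table 3 | medications, used for the whole table |
| Protocol Table 3, column heading | medications, products and procedures |

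**2. One case followed through the literal text**

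Suppose a participant has excimer laser to the scalp at Week 14.

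- If excimer laser is regarded as demonstrated to be effective for AA, the Protocol 6.4.2 sentence withdraws the participant from trial treatment.
- Protocol 9.3.2.4 and SAP 4.7.1.3 keep SALT values collected after treatment stops.
- Laser is not a medication on the ordinary meaning of the word, so the worst-observation and non-responder rules do not apply. The Week 24 SALT enters as observed.
- The sensitivity analyses (SAP 4.7.1.5 and 4.7.2.3) keep all available data by design, so they do not remove it either.

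**3. The plan's own figures, to set a scale**

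Inputs from SAP 2.3: reference mean reduction 58%, lower 95% bound about 42%, reference n=28, planned n=30.

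- SD = (58 − 42)/1.96 × √28 = 43.2 points
- SE = 43.2/√30 = 7.89 points
- Confidence in at least 42% when 58% is observed = Φ(16/7.89) = 0.979, against 0.98 in SAP Table 2.

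SAP Table 3 reproduces with the exact one-sided binomial, P(X ≤ x − 1 | n=30, p=0.27): 0.916 for 12/30, 0.839 for 11/30 and 0.577 for 9/30, against 0.92, 0.84 and 0.58 stated.

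**4. Difference between the two readings**

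The documents give neither the frequency of procedures nor the gain that follows them. Assume k of 30 participants have a procedure and an observed 60% reduction, which the rule would reset to 0%. The mean shifts by k × 60/30. The SD is held at 43.2.

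| k | Shift in mean | Mean, from 58% | Confidence in ≥42% |
|---|---|---|---|
| 1 | 2.0 points | 56.0% | Φ(14.0/7.89) = 0.96 |
| 2 | 4.0 points | 54.0% | Φ(12.0/7.89) = 0.94 |

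Over other assumed gains, the shift per participant is 30/30 = 1.0 point for a 30% reduction and 100/30 = 3.3 points for a 100% reduction. For a given observed reduction these shifts are minimums: the imputed value includes baseline among the candidates, so it cannot be better than 0%.

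For a responder rate, each reclassified participant moves it by 1/30 = 3.3 points, and two move it by 6.7. In SAP Table 3, going from 12 to 11 responders lowers confidence in at least 27% from 0.92 to 0.84. Going from 11 to 9 lowers it from 0.84 to 0.58.

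**The case against.** The strongest reply is that the protocol uses medications as an umbrella term. The sentence introducing Table 3 applies the word to the whole table, procedures included, and Protocol 7.1.1 says medications while pointing to the wider rule in 6.4.2. On that reading the medical monitor may put phototherapy or excimer laser on the list. This stands, and it rules out saying that the plan definitely excludes procedures or that they can never trigger the rule.

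A reader might also infer that procedures will go unrecorded. The documents do not establish that. Exclusion criteria 32 and 40 set timeframes for platelet-rich plasma and for phototherapy and laser, so the Protocol 6.4 sentence could reach them, and the eCRF and the programming plan are not available. However, those timeframes run back from Day 1, so they do not clearly secure dates for use during the trial.

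The Table 3 items are not equivalent. PUVA has a drug component, and platelet-rich plasma is injected and could be classed as a medication. Hair transplant and scalp micropigmentation turn on whether they are considered effective for AA, not on the word medications. The documents also do not say that micropigmentation would change a SALT score given by a qualified assessor.

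Finally, SAP 4.2 lists protocol deviations by participant, and SAP 4.7.2.2 plans plots of each participant's SALT over time. These may make a case visible, but they change no value in the analysis. It is also true that one participant's 2.0 points is about a quarter of the implied standard error (2.0/7.89 = 0.25), in a descriptive trial with no hypothesis test.

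**Conclusion.** The concern holds as a scope that is too narrow on its literal wording and otherwise unclear. The efficacy rules name only medications, the reporting section ties that phrase to drug coding, and the prohibition they serve is wider. UV-B phototherapy and excimer laser are the clearest cases, with PUVA close behind. Unless the broader reading is adopted, SALT after these procedures stays as observed in the primary and responder analyses, and no planned sensitivity analysis removes it.

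The size is illustrative only: 2.0 points on the mean per participant with an assumed 60% reduction, and 3.3 points on a rate per reclassified responder. These figures measure the gap between the two readings. They do not estimate bias, because part of such a reduction could be due to daxdilimab. A reader might infer that the reported effect will be inflated; without a rate of procedure use, the documents do not support that. The case for changing the text is that the scope of a pre-specified rule should not rest on interpretation in an open-label, single-arm trial of 30.

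**What to change.** - In Protocol 9.3.2.3 and SAP 4.7.1.3 and 4.7.2.2, make the trigger *any medication, product, therapy or procedure in Protocol Table 3 that is considered effective for AA*.
- State that the medical monitor's list covers procedures as well as drugs.
- In Protocol 6.4 and the eCRF, require such procedures during the trial to be recorded with dates. In SAP 4.8.4, list them beside the ATC table.
- Reconcile the wording of Protocol 6.4.2, 7.1.1 and 9.3.2.3, which alternate between medications alone and medications or therapies.
- Optionally, and as a separate decision, state whether SALT after a hair transplant or scalp micropigmentation is handled in the same way.

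The cost is a few lines of text and a small addition to data capture. The reported response may become slightly less favourable.
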